10.2.3.4 Genital infections

In clinical studies with licogliflozin, a small number of participants experienced non-serious, mild genital infections (mainly mycotic) with AEs including balanitis and vulvovaginal infections. This is observed due to dose dependent glucosuria as a consequence of SGLT2 inhibition. All genital infections reported in licogliflozin clinical trials were non-serious with the overall frequency similar to published reports for marketed SGLT2 inhibitors (dapagliflozin, canagliflozin).

Participants with symptomatic genital infection in the 4 weeks before randomization should be excluded. The possibility of genital infections (mainly mycotic like thrush) is described in the clinical study informed consent forms. Participants will be instructed to pay attention to genital hygiene and have appropriate hydration and be warned that severe genital infection may require urgent medical attention (see Section 10.2.3.8, Fournier's gangrene).

10.2.3.5 Hypoglycemia

Participants with T2DM treated with antidiabetic medications (especially insulin and sulfonylureas) are at risk of hypoglycemia. Licogliflozin is effective in reducing glucose level and may lead to hypoglycemia in participants receiving other antidiabetic medications (especially insulin and insulin secretagogue). Diabetic participants must continue their routine self-monitoring of glucose levels and be educated regarding hypoglycemic symptoms (dizziness, lightheadedness; palpitations, heart racing/pounding, shaking, sweating, hunger, blurred vision, impairment of motor function, confusion), explanation of possible triggers (strenuous exercise, delayed meals, changes in meal composition, illness, periods of prolonged fasting) and treatment by the physician managing the participant's diabetes.

Novartis	Confidential	Page 129 of 160
Amended Protocol Version 02 (Clean)		Protocol No. CLJN452D12201C
		44 4 44 4

During the course of the study, if a participant experiences clinically symptomatic hypoglycemia, an immediate medical evaluation should be conducted. Glucose levels will be measured. If a confirmed glucose level is <56 mg/dL by repeated measurement, background anti-diabetic medication may require dose adjustment, or study treatment may be interrupted and the participant treated according to standard of care for hypoglycemia.

Events consistent with or suspected to be hypoglycemia, should be recorded in the participant diary and on the AE eCRF.

Furthermore, this study outlines inclusion and exclusion criteria to minimize this risk and exclude participants at risk of this adverse event (please refer to Section 5 for details).

10.2.3.6 Pancreatitis

In the 2012 update to the diagnosis Atlanta classification of acute pancreatitis, 2 of the following 3 features are required for diagnosis: (1) abdominal pain consistent with acute pancreatitis (acute onset of a persistent, severe, epigastric pain often radiating to the back), (2) serum lipase (or amylase) activity at least 3 times greater than the upper limit of normal (ULN), and (3) characteristic findings of acute pancreatitis on contrast-enhanced computed tomography, magnetic resonance imaging or transabdominal ultrasonography. (Banks et al 2012) Therefore, in the event of AE of significant abdominal pain or other suggestive features, consider whether the participant may have pancreatitis; amylase and lipase should be checked and the need for diagnostic imaging considered. If pancreatitis is confirmed by this definition, the event must be reported as an SAE even if hospitalization is not required. All tests and procedures related to the diagnosis and treatment of the event should be recorded in the appropriate eCRFs. The acute episode should be managed as in normal clinical practice. Study medication may be interrupted during investigation of the event. If pancreatitis is confirmed, licogliflozin and other potentially suspect medicinal products should be discontinued.

10.2.3.7 Ketoacidosis

Euglycemic ketoacidosis is a rare adverse event reported with SGLT-2 inhibitor class of drugs. Participants are advised to maintain hydration and avoid excessive alcohol consumption. Participants should seek medical attention immediately in case they develop any of the following symptoms: vomiting, dehydration, labored breathing, unusual fruity smell in breath, tachycardia, confusion or disorientation and/or coma. Please note that blood glucose levels may be normal in this condition. Laboratory investigations for ketones, electrolytes and anion gap must be performed immediately. The participant must be hospitalized and managed for ketoacidosis as in normal clinical practice. Study medication should be interrupted and precipitating factors must be identified. Participants are advised to interrupt study medication in situations which can predispose ketoacidosis such as during prolonged fasting due to illness or surgery. If ketoacidosis is confirmed, the event must be reported as an SAE. All tests and procedures related to the diagnosis and treatment of the event should be recorded in the appropriate eCRFs.

10.2.3.8 Fournier's Gangrene

Fournier's gangrene is a rare adverse event reported with SGLT-2 inhibitor class of drugs. Participants are advised to pay attention to genital hygiene. Participants developing fever with pain or swelling in genital or anal region or any other signs/symptoms of infection of genitalia

Novartis	Confidential	Page 130 of 160
Amended Protocol Version 02 (Clean)		Protocol No. CLJN452D12201C
or perineum must seek medical advice immediately. Prompt treatment (including antibiotics		
and consideration of surgical debridement) should be instituted. Study medication should be		
discontinued. If the diagnosis of Fournier's gangrene is confirmed, the event must be reported		
as an SAE. All tests and procedures rela	ted to the diagnosis a	ind treatment of the event should

10.3 Committees

10.3.1 Data Monitoring Committee

be recorded in the appropriate eCRFs.

This study will include an external Data Monitoring Committee (DMC) which will function independently of all other individuals associated with the conduct of this clinical trial, including the site investigators participating in the study. The committee will consist of at least two physicians and a statistician who are not otherwise associated with the study, and who are experienced in multicenter trials in hepatology, metabolic disorders or general medicine. The main tasks of the committee for this study will be to review emerging safety data and primary efficacy data and provide recommendations to the sponsor concerning safety.

The Data Monitoring Committee charter provides detail on the committee composition and processes.

The DMC will review safety, including AEs and laboratory parameters, on a regular basis. In addition, in the event that more than 3 participants develop similar SAEs, or otherwise if found necessary by the sponsor, the DMC chairman will be alerted. Further details regarding relevant data and actions will be specified in the separate DMC charter.

11 Data Collection and Database management

11.1 Data collection

Designated investigator staff will enter the data required by the protocol into the electronic Case Report Forms (eCRF). The eCRFs have been built using fully validated secure web-enabled software that conforms to 21 CFR Part 11 requirements, Investigator site staff will not be given access to the EDC system until they have been trained. Automatic validation programs check for data discrepancies in the eCRFs, allow modification and/or verification of the entered data by the investigator staff.

The investigator/designee is responsible for assuring that the data entered into eCRF is complete, accurate, and that entry and updates are performed in a timely manner. The Investigator must certify that the data entered are complete and accurate

After final database lock, the investigator will receive copies of the participant data for archiving at the investigational site.

All data should be recorded, handled, and stored in a way that allows its accurate reporting, interpretation, and verification.

11.2 Database management and quality control

Novartis personnel or designated contract research organization (CRO) will review the data entered by investigational staff for completeness and accuracy. Electronic data queries stating

Novartis

Confidential

Amended Protocol Version 02 (Clean)

the nature of the problem and requesting clarification will be created for discrepancies and missing values and sent to the investigational site via the EDC system. Designated investigator site staff are required to respond promptly to queries and to make any necessary changes to the data.

Concomitant treatments and prior medications entered into the database will be coded using the World Health Organization (WHO) Drug Reference List, which employs the Anatomical Therapeutic Chemical classification system. Medical history/current medical conditions and adverse events will be coded using the Medical Dictionary for Regulatory Activities (MedDRA) terminology.

Dates of screenings, randomizations, screen failures and study completion, as well as randomization codes and data about all study treatment (s) dispensed to the participant and all dosage changes will be tracked using an Interactive Response Technology (IRT). The system will be supplied by a vendor, who will also manage the database. The data will be sent electronically to Novartis or a designated CRO at specific timelines.

Each occurrence of a code break via IRT will be reported to the clinical team and monitor. The code break functionality will remain available until study shut down or upon request of Novartis.

Once all the necessary actions have been completed and the database has been declared to be complete and accurate, it will be locked **and the treatment codes will be unblinded** and made available for data analysis. Any changes to the database after that time can only be made after written agreement by Novartis development management.

11.3 Site monitoring

Before study initiation, at a site initiation visit or at an investigator's meeting, a Novartis/delegated CRO representative will review the protocol and data capture requirements (i.e. eCRFs) with the investigators and their staff. During the study, Novartis employs several methods of ensuring protocol and GCP compliance and the quality/integrity of the sites' data. The field monitor will visit the site to check the completeness of participant records, the accuracy of data capture / data entry, the adherence to the protocol and to Good Clinical Practice, the progress of enrollment, and to ensure that study treatment is being stored, dispensed, and accounted for according to specifications. Key study personnel must be available to assist the field monitor during these visits. Continuous remote monitoring of each site's data may be performed by a centralized Novartis/delegated CRO/CRA organization. Additionally, a central analytics organization may analyze data & identify risks & trends for site operational parameters, and provide reports to Novartis clinical teams to assist with trial oversight.

The investigator must maintain source documents for each participant in the study, consisting of case and visit notes (hospital or clinic medical records) containing demographic and medical information, laboratory data, electrocardiograms, and the results of any other tests or assessments. All information on eCRFs must be traceable to these source documents in the participant's file. The investigator must also keep the original informed consent form signed by the participant (a signed copy is given to the participant).

The investigator must give the monitor access to all relevant source documents to confirm their consistency with the data capture and/or data entry. Novartis monitoring standards require full verification for the presence of informed consent, adherence to the inclusion/exclusion criteria,

Novartis	Confidential	Page 132 of 160
Amended Protocol Version 02 (Clean)		Protocol No. CLJN452D12201C

documentation of SAEs, and of data that will be used for all primary variables. Additional checks of the consistency of the source data with the eCRFs are performed according to the study-specific monitoring plan. No information in source documents about the identity of the participants will be disclosed.

12 Data analysis and statistical methods

A final analysis will be conducted after all participants finish the end of study or premature study discontinuation visit. No interim analysis for earlier statistical inference is planned for the study. Analyses for DMC review will be outlined in a separate DMC charter.

Unless if specified differently, descriptive analysis for categorical data will be summarized as frequencies and percentages and continuous data will be summarized with the mean, standard deviation, median, minimum, and maximum.

Any data analysis carried out independently by the investigator should be submitted to Novartis before publication or presentation.

12.1 Analysis sets

Following analysis populations will be defined for the statistical analysis:

Screened analysis set (SCR) comprises of all participants who signed the informed consent.

Randomized Analysis set (RAN) comprises of all participants who received a randomization number, regardless of whether participants received study medication.

Full Analysis Set (FAS) comprises of all participants to whom study treatment has been assigned by randomization. Participants who were mis-randomized (not qualified for randomization but randomized inadvertently) and did not receive investigational medication, however, are excluded from the FAS. Efficacy analysis will be conducted on FAS. Following the intent-to-treat (ITT) principle, participants are analyzed according to the treatment they have been assigned during the randomization procedure regardless of actual treatment received and the true stratum the participant belongs to if a participant is assigned to wrong stratum during randomization.

Safety Analysis Set (SAF) includes all participants who received at least one dose of study treatment. Participants will be analyzed according to the study treatment received, where treatment received is defined as the randomized/assigned treatment if the participant took at least one dose of that treatment or the first treatment received if the randomized/assigned treatment was never received.

The number of participants in each analysis set will be presented by treatment group and overall for the screen set.

The number and percentage of participants in the randomized set who completed the study, who discontinued the study and the reason for discontinuation will be presented for each treatment group and all participants. The frequency (%) of participants with protocol deviations and criteria leading to their exclusion from each analysis set will be presented for randomized set.

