At the time of preparation of this protocol amendment (V01) document, 225 participants have been screened and 27 participants randomized as of 18-Sep-2020.

Protocol Section	Change	Rationale for change
Protocol title	From: A randomized, double-blind, parallel-group, multicenter study to assess efficacy, safety, and tolerability of oral tropifexor (LJN452) & licogliflozin (LIK066) combination therapy, compared to each monotherapy, for treatment of adult patients with nonalcoholic steatohepatitis (NASH) and liver fibrosis (ELIVATE) To:	A Placebo treatment group has been added to the study and the title change reflects that all active treatment groups will be compared to placebo.
	A randomized, double-blind, parallel-group, multicenter study to assess efficacy, safety, and tolerability of oral tropifexor (LJN452) & licogliflozin (LIK066) combination therapy, and each monotherapy, compared with placebo for treatment of adult participants with nonalcoholic steatohepatitis (NASH) and liver fibrosis (ELIVATE)	

Changes to the Protocol

Novartis Amended Proto	Confidential Pag pcol Version 02 (Clean) Protocol No. CLJN45	e 27 of 160 2D12201C
Protocol Section	Change	Rationale for change
List of abbreviations	New abbreviations added or deleted	Updated to align with the revised protocol
Protocol Summary	Updates made to all sections of the summary. Details and rationale for each change in the summary can be found in the respective sections of this Amendment summary.	To align with the changes made to the body of the protocol.

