Section 3	Updated first paragraph as follows: This is a randomized, double-blind, parallel-group, multiple-arm study to assess the efficacy, safety and tolerability of tropifexor and licogliflozin combination therapy, and each monotherapy compared with placebo as well as the combination therapy compared to each monotherapy, in participants with NASH and fibrosis. Study design updated as follows: Approximately 380 participants with NASH (NAS ≥4) and fibrosis stage 2 or 3 will be randomly assigned to one of the following treatments: Arm A: Combination therapy Arm - (N=140): tropifexor 140 µg + licogliflozin 30 mg, once daily. Arm B: Tropifexor monotherapy Arm - (N=80): tropifexor 140 µg (+ placebo matching licogliflozin), once daily. Arm C: Licogliflozin monotherapy Arm - (N=80): licogliflozin 30 mg (+ placebo matching tropifexor), once daily. Arm D: Placebo Arm – (N=80): placebo matching tropifexor + placebo matching licogliflozin once daily.	Include a placebo arm to minimize sources of bias and to ensure reliable inference with respect to the safety and effectiveness of the treatment as prompted by: 1. Strong recommendati on from DMC and HAs during the initial review of the protocol 2. Recent trials which have shown unexpectedly high placebo response rates, raising concerns about the interpretability of outcomes in a

	cocol Version 02 (Clean) Protocol No. CLJN45	
Protocol Section	Change	Rationale for change
		non-placebo controlled trial.
		Increase sample size to accommodate addition of placebo arm, change of hypothesis tests, update in response rate assumptions and to increase statistical power.
Figure 3- 1Study Design	New figure: N= 380 (1.75:1:1:1) Screening liver biopsy Iver eligibility biopsy NASH with fibrosis Screening liver Screening liver Screening e-6 months pseline Screening (1:0weeks) Baseline End of Study (Biopsy)	Figure updated to reflect new sample size and study design, including addition of placebo treatment group, increase in sample size from 210 to 380, and randomization ratio change from 1:1:1 to 1.75 (combination) : 1 (tropifexor) : 1 (licogliflozin) :1 (placebo).

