Section 5.1	Inclusion Criterion 3 revised to specify that the NAFLD Activity Score (NAS) for eligible participants must be >= 4 with at least 1 point each in inflammation and ballooning on the screening histology assessment performed by the central reader.	Requested by the US Food and Drug Administration (FDA) during the IND review.
Section 5.2	Exclusion Criterion 4: updated as follows: History of hypersensitivity to either of the study drugs or their excipients or to drugs of similar chemical classes, or participants with hereditary galactose intolerance, lactase deficiency or glucose-galactose malabsorption	Requested by BfArM (Bundesinstitut für Arzneimittel und Medizinprodukte - The Federal Institute for Drugs and Medical Devices) and the German Ethics Committee during the Clinical Trial Application (CTA) review.
	 Exclusion Criterion 5: Updated as follows: Taking a permitted medication listed in Table 6-2 but who is NOT on a stable dose (within 25% of baseline dose) from the start of the screening. period and a. for at least 3 months prior to the baseline visit for thyroid hormone, oral anti-diabetic medication, insulin, and GLP-1 agonists b. for at least 6 months prior to baseline for Vitamin E 	Requested by the US Food and Drug Administration (FDA) during the IND review.
	Exclusion Criterion 6: revised to add "unit of alcohol", commonly used in some participating countries as follows: Significant alcohol consumption is defined as more than 20 g/day (14 units/week) in females, or more than 30 g/day (21 units/week) in males, on average. A "unit" of alcohol is equivalent to one (12-ounce; 355 ml) beer, one glass (4-ounce; 120 ml) of wine, or 1 shot (ounce; 30 ml) of hard liquor.	Requested by the US Food and Drug Administration (FDA) during the IND review.
	Exclusion Criterion 7: definition of uncontrolled type 2 diabetes reduced from HbA1c >= 9.5% to HbA1c >= 9.0%	Requested by the US Food and Drug

Protocol	Change	Rationale for
Section		change
		Administration (FDA) during the IND review.
	Exclusion Criterion 8: exclusionary value for platelets is < LLN (lower limit of normal) and refers to central laboratory normal range and not a specific numeric value.	Requested by th US Food and Drug Administration (FDA) during the IND review.

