	Table 16-5 time for collection of 'post previous evening dose' samples updated to 'Recommended 18h (+/- 4h)'.	Timing for sample collection is aligned with protocol Section 8.5.2.

Editorial changes throughout the document for clarity.

A copy of this amended protocol will be sent to the Institutional Review Board (IRBs)/Independent Ethics Committee (IECs) and Health Authorities. The changes described in this amended protocol require IRB/IEC approval prior to implementation. The Informed Consent has been adapted accordingly to reflect the above changes.

Amended Protocol Version 02 (Clean) No additional risks related to COVID-19 pandemic were identified, and therefore the benefit risk is unchanged.

Protocol summary

Protocol number	CLJN452D12201C		
Full Title	A randomized, double-blind, parallel-group, multicenter study to assess efficacy, safety, and tolerability of oral tropifexor (LJN452) & licogliflozin (LIK066) combination therapy, and each monotherapy, compared with placebo for treatment of adult participants with nonalcoholic steatohepatitis (NASH) and liver fibrosis (ELIVATE)		
Brief title	Study to assess efficacy, safety, and tolerability of oral tropifexor (LJN452) & licogliflozin (LIK066) combination therapy, and each monotherapy, compared with placebo (ELIVATE)		
Sponsor	Novartis Pharma AG		
Investigation type	Drug		
Clinical Phase	Phase IIb		
Study type	Interventional		
Purpose	To compare tropifexor and licogliflozin in combination therapy and each monotherapy, to placebo for efficacy, safety, and tolerability in participants with NASH and liver fibrosis (stage 2 or 3) as per NASH CRN histological score.		
Primary Objective(s)	To evaluate the efficacy of tropifexor + licogliflozin in combination therapy and each monotherapy treatment, as assessed by histologic improvement after 48 weeks compared to placebo in participants with NASH and stage 2 or 3 fibrosis.		
Secondary Objectives	• To evaluate the efficacy of combination therapy and two monotherapies in NASH or fibrosis with a composite endpoint after 48 weeks of treatment.		
	• To evaluate improvement in fibrosis by at least one stage after 48 weeks of treatment.		
	• To evaluate improvement in fibrosis by at least two stages with no worsening of NASH after 48 weeks of treatment.		
	• To evaluate reduction in body weight from Baseline after 48 weeks of treatment.		
	• To evaluate change in liver fat content after 48 weeks of treatment.		

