6.1.3 Treatment arms/group

Participants (n = 380) will be assigned at Baseline visit to one of the following 4 treatment arms in a ratio of 1.75:1:1:1 in a blinded manner. Placebo capsules/tablets will be given in each treatment arm where necessary to maintain blinding.

Arm A: Combination therapy Arm - (N=140): tropifexor 140 μ g + licogliflozin 30 mg, once daily.

Arm B: Tropifexor monotherapy Arm - (N=80): tropifexor 140 μ g (+ placebo matching licogliflozin), once daily.

Arm C: Licogliflozin monotherapy Arm - (N=80): licogliflozin 30 mg (+ placebo matching tropifexor), once daily.

Arm D: Placebo Arm – (N=80): placebo matching tropifexor + placebo matching licogliflozin, once daily.

The 140 μ g dose of tropifexor and its matching placebo are each now available as a single hard gelatin capsule. Participants participating at the time of availability of the single tropifexor/placebo capsule, may continue on the 3-capsule tropifexor (100 μ g + 30 μ g + 10 μ g) or matching placebo regimen until the available 3- capsule supply is depleted. After the 3-capsule tropifexor or matching placebo supply is depleted, participants will take one 140 μ g tropifexor or matching placebo capsule daily. No change is made to licogliflozin dosing. Further details can be found below and in Section 6.7.2.

6.1.3.1 Dosing with 3 capsule $(10 + 30 + 100 \mu g)$ tropifexor supply

Until 3-capsule tropifexor ($100 \ \mu g + 30 \ \mu g + 10 \ \mu g$) and matching placebo is replaced by the 140 μg hard gelatin single capsule, in order to maintain the blind, placebo capsules matching tropifexor (LJN452) 10, 30 and 100 μg and placebo tablets matching licogliflozin (LIK066) 10 mg will be given to participants as indicated in Table 6-5, so that all participants will receive 3 capsules and 3 tablets per day. **One capsule from each of the 3 bottles**, and **3 tablets from the blister pack** should be taken close to the evening meal; either just prior to (within 5 minutes) consuming the evening meal, or no more than 30 minutes after consuming the evening meal and at about the same time each day.

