Combination vs. placebo (test 1, k = 1, i = Cmb, j = Plc)

Tropifexor (LJN452) vs. placebo (test 2, k = 2, i = LJN, j = Plc); licogliflozin (LIK066) vs. placebo (test3, k = 3, i = LIK, j = Plc)

Combination vs. tropifexor (LJN452) (test 4, k = 4, i = Cmb, j = LJN); combination vs. licogliflozin (LIK066) (test 5, k = 5, i = Cmb, j = LIK)

There are ten potential tests to be performed for the two primary endpoints (five for each primary endpoint), and it is important to control the overall Type I error rate for these tests. The alpha recycling graph presented in Figure 12-1 shows how alpha transfers among them. If the data fails to reject the null hypothesis of a test, then the alpha of that test will not be passed to others. This restriction ensures the control of overall Type I error rate. Again, for the primary

Confidential

Amended Protocol Version 02 (Clean) Protocol No. CLJN452D12201C endpoints, the overall alpha is set at two-sided 5%. A logistic regression model with the logit of probability for histological response as the dependent variable, treatment groups as the main effect, baseline fibrosis stage and T2DM (No/Yes) as explanatory variables, and the baseline BMI as a covariate will be utilized to test the hypotheses at each step. While this model will be the typical logistic regression in most cases, it should be set as the Firth logistic regression if some arm (such as the placebo) has a low response rate, as the Firth method returns less biased results for data with rare events. The null hypothesis of *k*th test, if executed, will be rejected if the p-value for the coefficient of treatment effect in the *k*th comparison is less than or equals to its corresponding alpha. If no alpha is passed to a specific comparison, then its corresponding test will not be performed and p-value will not be calculated. More statistical specifications of the model will be described in the statistical analysis plan (SAP).

The number and percentages of histological responders at week 48 in FAS will be summarized by treatment groups. The difference between the treatment of interest and the alternative treatment will be presented along with 95% confidence interval calculated based on the normal approximation for distribution of the difference between two binomial random variables.

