# 1.1 Study design

[figure not shown]
This is a randomized, double-blind, parallel-group, multiple-arm study to assess the efficacy, safety and tolerability of tropifexor and licogliflozin combination therapy compared to each monotherapy in patients with non-alcoholic steatohepatitis (NASH) and advanced fibrosis.

The study consists of 1) a screening period, 2) a treatment period starting from randomization on Day 1 and running to Week 48, and 3) a follow-up period of 4 weeks after the last dose of study treatment. The screening period starts from the time of the signing informed consent and continues for up to 8 weeks when all inclusion/exclusion criteria have been evaluated and all baseline assessments have been performed. The study duration from first dose of study medication is 52 weeks. The total duration of participation may be up to 60 weeks.

Approximately 210 patients with NASH and F2-F3 fibrosis will be randomized in a 1:1:1 ratio to one of the following treatments:

- Arm A: tropifexor + licogliflozin combination therapy,
- Arm B: tropifexor monotherapy,
- Arm C: licogliflozin monotherapy

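### Placebo comparisons pool active-arm participants randomised before the placebo arm existed, with no term for randomisation scheme and no concurrent-only analysis

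*Protocol*

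**What the plan says.** The SAP (section 1.1, dated 09-Dec-2019) gives the original design: "Approximately 210 patients with NASH and F2-F3 fibrosis will be randomized in a 1:1:1 ratio to one of the following treatments", all of them active.

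Amendment 01 added the placebo arm and moved allocation to 1.75:1:1:1. Its rationale records that "225 participants have been screened and 27 participants randomized as of 18-Sep-2020". It closes with "The changes described in this amended protocol require IRB/IEC approval prior to implementation", so 27 is a minimum for the number randomised under the old scheme.

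Current protocol text:
- **Section 12.1.** The "Full Analysis Set (FAS) comprises of all participants to whom study treatment has been assigned by randomization". The only exclusion is for mis-randomised participants who received no study drug.
- **Section 12.4.2.** The primary logistic model has "treatment groups as the main effect, baseline fibrosis stage and T2DM (No/Yes) as explanatory variables, and the baseline BMI as a covariate".
- **Section 6.1.3.** "Participants (n = 380) will be assigned at Baseline visit to one of the following 4 treatment arms". Nothing says whether those randomised before the change are part of the 380.

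No passage limits the placebo comparisons to concurrently randomised participants, adjusts for scheme or period, or plans a sensitivity analysis on this point.

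**The concern.** Participants from the three-arm period can only be in active arms. If they respond differently from later participants for reasons unrelated to treatment, the difference enters every active-vs-placebo contrast, and randomisation does not protect against it. Combination vs monotherapy is touched too, because the ratio changed from 1:1 to 1.75:1 and early entrants make up different shares of those arms.

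A period difference is plausible. Amendment 01 also revised eligibility, for example "definition of uncontrolled type 2 diabetes reduced from HbA1c >= 9.5% to HbA1c >= 9.0"%. It also specified at least one point each for inflammation and ballooning, and revised the platelet, albumin, bilirubin, INR and MELD exclusions. How many of the 27 entered under looser criteria is not documented, because some of these changes had already been made through country-specific amendments.

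At stake is the comparison the amendment was written to make possible: placebo was added to reduce bias, and the first test in each primary branch is combination vs placebo.

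**Working it through.** **Inputs.** 27 early entrants (Amendment 01 rationale); allocation 1.75:1:1:1 and 380 in total (6.1.3); response rates and correlation 0.5 (12.8.1, Table 12-3); two-sided 5% split evenly over two endpoints (12.4.2), which is 0.0125 in the upper tail per endpoint. Assumptions: the 27 split 9:9:9, and early response differs from later response by 10 or 20 points.

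**The plan's own figure.** Simulating the two correlated endpoints with an unpooled z-test reproduces the Table 12-5 power of 0.85 at 140 vs 80, and 0.80 at 95 vs 95. That calculation treats 140 vs 80 as a single concurrent randomisation.

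**Arm sizes and early shares** (combination/monotherapy/monotherapy/placebo)
- 27 inside the 380: 353 × 1.75/4.75 = 130.1 and 353/4.75 = 74.3. Adding 9 per active arm gives about 139/83/83/74. Early share: 9/139 = 6.5% of combination, 9/83 = 10.8% of each monotherapy, 0% of placebo.
- 27 on top of the 380: 149/89/89/80. Early share: 9/149 = 6.0%, 9/89 = 10.1%, 0%.

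**Shift in the crude difference** = (early share in first arm − early share in second arm) × period difference

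| Contrast | 10 points | 20 points |
|---|---|---|
| Combination vs placebo | 0.6 | 1.2-1.3 |
| Monotherapy vs placebo | 1.0-1.1 | 2.0-2.2 |
| Combination vs monotherapy (opposite sign) | 0.4 | 0.8-0.9 |

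**Upper-tail error, pooled z, nominal 0.0125.** 1,000,000 trials per cell, null rates 10% and 20%, both arm-size cases:

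| Early minus later | Combination vs placebo | Monotherapy vs placebo* |
|---|---|---|
| 0 | 0.009-0.011 | 0.011-0.013 |
| +10 | 0.013-0.015 | 0.019 |
| +20 | 0.018-0.019 | 0.027-0.031 |
| −10 | 0.006-0.008 | 0.006-0.008 |

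*Illustrative: the Figure 12-1 weights are not in the text, and the test is treated as unconditional.

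If 60 had entered early (assumption; 20 per active arm), the combination figure at +10 is about 0.020.

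**Firth logistic Wald test.** Combination vs placebo, 139/83/83/74, no baseline covariates, 20,000 trials per cell, null 10% / 20%:

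| Early minus later | No scheme factor | With scheme factor |
|---|---|---|
| 0 | 0.0024 / 0.0073 | 0.0031 / 0.0072 |
| +10 | 0.0044 / 0.0098 | 0.0029 / 0.0080 |
| +20 | 0.0058 / 0.0125 | 0.0027 / 0.0070 |

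**What the factor does.** In the linear analogue with a scheme factor, the early combination participants keep a weight of 0.042 in combination vs placebo, offset by −0.021 on each early monotherapy group. The early weights sum to zero, so an additive period shift cancels. The early data still contribute, so the contrast is not purely concurrent.

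**The case against.** The strongest reply is that the effect is too small to justify changing the primary model.

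- **Firth test.** Section 12.4.2 provides for Firth when an arm has a low response rate, and the SAP specifies it. At +10, combination error under Firth stays below 0.0125. Only at +20 does it reach about nominal; a separate two-group Firth check gives 0.0138 at the 20% null.
- **Monotherapy figures.** These tests run only after combination has beaten placebo on that endpoint, and the two in a branch may share its alpha. A Firth check at 0.0125 gives 0.009/0.014 at +10 and 0.016/0.021 at +20 (null 10%/20%). At an illustrative 0.00625, the +10 figures are about 0.003/0.006.
- **Size of drift.** Nothing in the documents supports a particular value, and +20 would double or triple a null rate of 20% or 10%. The model already adjusts for fibrosis stage, T2DM and BMI. Per the Amendment 02 change table, biopsies are also re-read as temporally blinded pairs at trial completion, which limits reader drift.
- **Age of the SAP.** It predates Amendment 01 and says it may be amended, and the protocol leaves model detail and sensitivity analyses to it.

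Most of this stands as a limit on size: at 27 the inflation is modest, and the monotherapy figures are illustrations. It does not remove the bias. A conservative test still reports a shifted odds ratio, covariate adjustment and paired re-reading address only some sources of a period difference, and the true number of early entrants is not given. That the SAP has to be rewritten for four arms makes it the natural place for the change.

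**Conclusion.** The concern holds. As written, the plan mixes non-concurrent active participants into every placebo contrast without adjustment or a check. With 27 early entrants split 9:9:9, the shift per 10 points of period difference is about 0.6 points for combination vs placebo and 1.0-1.1 for monotherapy vs placebo, with unknown sign. Type I error moves modestly, and under Firth the combination test stays at or near nominal. The size rests on the assumed split and drift, and it grows with the number randomised before the four-arm scheme started. This should be fixed, but it does not by itself threaten the trial. An all-randomised FAS is ordinary practice; the gap is in the model and the sensitivity plan.

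**What to change.** 1. Add randomisation scheme (three-arm vs four-arm) as a factor in the primary and key secondary logistic models, in protocol 12.4.2 and in the four-arm SAP update. This removes an additive period shift but does not make the placebo contrasts concurrent-only.
2. Add a sensitivity analysis of the placebo comparisons restricted to participants randomised under the four-arm scheme.
3. State whether participants randomised before that scheme count in the 380.

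**Cost.** One factor, one table and one sentence, to be specified before unblinding. With the 27 inside the 380:
- The factor raises the standard error by about 0.4% for combination vs placebo and 0.9% for each monotherapy vs placebo (linear analogue).
- The restricted analysis raises it by √[(1/130 + 1/74)/(1/139 + 1/74)] − 1 = 1.2% and √[(1/74 + 1/74)/(1/83 + 1/74)] − 1 = 2.8%.
- Power for combination vs placebo on at least one endpoint is 0.83 for the full FAS and 0.82 restricted.

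If the 27 are on top of the 380, power is 0.85 for both.
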